10.7.2 Retrieval or destruction

All partially used or unused treatments will be verified by the Sponsor. A detailed treatment log of the returned Investigational Product will be established with the Investigator (or the pharmacist) and countersigned by the Investigator (or the Pharmacist) and the Sponsor representative. The Investigator (or the pharmacist) will not destroy the unused Investigational Product unless the Sponsor provides written authorization. In case of a potential defect in the quality of Investigator will be responsible for promptly addressing any request made by the Sponsor, in order to recall Investigational Product and eliminate potential hazards.

10.7.3 Accountability and compliance

The investigator, or a responsible party designated by the investigator, must maintain a careful record of the inventory and disposition of all agents received from DCTD using the NCI Drug Accountability Record Form (DARF). (See the NCI Investigator's Handbook for Procedures for Drug Accountability and Storage.)

The investigator or pharmacist will inventory and acknowledge receipt of all shipments of the investigational product. The investigator or pharmacist will also keep accurate records of the quantities of the study treatments dispensed and used for each patient, to assess the patient treatment compliance. The sponsor representative will periodically check the supplies of investigational products held by the investigator or pharmacist to verify accountability of all investigational products used. All unused investigational products and all medication containers will be destroyed by the study sites. The Sponsor will verify that a final report of drug accountability at the unit dose level is maintained and archived in the investigator study file. Administration of the study treatment will be supervised by the investigator or sub-investigator.

10.8 Concomitant treatment restrictions

10.8.1 Medications prohibited for enrollment and the duration of the study

Experimental antiretroviral agents or those containing zidovudine (including Combivir and Trizivir) or ritonavir (including Kaletra), Cobicistat or similar potent CYP3 inhibitors are prohibited for enrollment and the duration of the study.

10.8.2 Potential Drug Interactions of Brentuximab Vedotin

In vitro data, one of SGN-35 active metabolites, monomethyl auristatin E (MMAE) is a substrate and an inhibitor of CYP3A4 but is not a sensitive substrate nor a strong inhibitor/inducer of CYP3A4. However, patients should be monitored for potential drug-interaction when administered drugs known to be a strong CYP 3A4 inhibitor/inducer with SGN-35. In vitro, MMAE is a substrate of P-gp transporter and is not an inhibitor of P-gp.

10.9 Reporting requirements for concomitant medications

All medications must be reported in the site's source documents at baseline. All medications will be reviewed and updated in the site's source documents at all visits where indicated in the schedule of evaluations (Appendix I). Only a subset of medications will be reported in the Concomitant Medications CRFs after study entry, as listed below:

- 1. Anti-seizure medications
- 2. Prophylactic medications
 - Antiviral
 - Antifungal
 - Quinolone/Antibiotic therapy
 - Any other medications used for prophylaxis of opportunistic infections
- 3. Hepatitis medications
- 4. Growth colony stimulation factors (GCSF)
- 5. Erythropoiesis Stimulating Agents (ESA)
- 6. Anti-retroviral medications. Note: Antiretroviral therapy will be collected in the On Study Form. If the subject remains on the same anti-retroviral medications throughout study participation that have already been reported in the On Study Form, then do not report them in the Concomitant Medications Form. If the subject changes or discontinues anti-retroviral therapy for any reason, then update the Concomitant Medication Form with the start and stop date of the discontinued medication(s) and start date of the new (if applicable) medication(s).
- 7. Receipt of disallowed medications (CYP3A4 or P-glycoprotein inhibitors) after study enrolment, as per Appendix 20.9.

10.10 Prophylactic measures

10.10.1 Growth Factor

GCSF will be administered on Days 2-10 and 16-24 throughout each 28-day cycle using standard doses. Pegfilgrastim may be substituted for GCSF and administered on days 2 and 16.

10.10.2 Pneumocystis prophylaxis

Trimethoprim sulfamethoxazole (Bactrim) (one double strength tablet twice daily three days per week or one single strength daily) must be given at the onset of therapy for Pneumocystis and Toxoplasmosis prophylaxis. Alternatively, dapsone (50 mg PO twice daily), atovaquone, or aerosolized pentamidine may be substituted for Pneumocystis prophylaxis in subjects allergic to sulfonamides. Pneumocystis prophylaxis will be continued once therapy has been discontinued.

10.10.3 Mycobacterium avium complex (MAC) prophylaxis

Azithromycin 1,200 mg PO once weekly must be initiated for prophylaxis if the CD4 count falls below 50 cells/ μ L or is expected to drop below 50 cells/ μ l while on chemotherapy. Prophylaxis may be discontinued once the CD4 count is deemed reliably above 50 cells/ μ L by the treating investigator.

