4.4.4 Mycobacterium avium complex (MAC) prophylaxis

Azithromycin 1,200 mg PO once weekly must be initiated for prophylaxis if the

CD4 count falls below 50 cells/ μ L or is expected to drop below 50 cells/ μ l while on chemotherapy. Prophylaxis may be discontinued once the CD4 count is deemed reliably above 50 cells/ μ L by the treating investigator.

Due to the glycoprotein P inhibition properties of azithromycin, this may increase the chemotherapy drug exposure and contribute to increased toxicity. Sections 3.1.19, 7.3.7, and Appendix XIII state that P-glycoprotein inhibitors, including azithromycin, are disallowed medications on protocol. This limited exception is permitted in the case of MAC prophylaxis.

Based on the pharmacokinetics of azithromycin and brentuximab vedotin, the study team recommends giving the azithromycin on Days 5, 12, 19, and 26 of each cycle.

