 - Other strong CYP3A inhibitors.
 - Moderate CYP3A4 inhibitors should be used with Caution but are not excluded. If 2 moderate CYP3A4 inhibitors are used concurrently, one must be discontinued at least 7 days (1 week) prior to the initiation of chemotherapy.
 - P-glycoprotein inhibitors.
 - If patients are taking any of these excluded medications, they must be discontinued at least 7 days (1 week) prior to the initiation of chemotherapy.

All concomitant medications must be reviewed by the study chair or co-chair prior to enrollment by email.

Because the lists of these agents are constantly changing, it is important to regularly consult a frequently-updated medical reference for a list of drugs to avoid or minimize use of.

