Strong CYP3A inhibitors and P-glycoprotein inhibitors must be discontinued 7 days prior to therapy. Moderate CYP3A4 inhibitors should be used with Caution but are not excluded. If 2 moderate CYP3A4 inhibitors are used concurrently, one must be discontinued at least 7 days prior to chemotherapy.

Because the lists of these agents are constantly changing, it is important to regularly consult a frequently-updated medical reference for a list of drugs to avoid or minimize use of.

P-Glycoprotein Inhibitors	Strong CYP 3A4	Moderate CYP 3A4
	Inhibitors	Inhibitors
Antiretrovirals	Antiretrovirals	Antiretrovirals
Lopinavir and ritonavir	Cobicistat	Atazanavir
	Indinavir	
Other Agents	Nelfinavir	Other Agents
Amiodarone	Ritonavir	Aprepitant
Azithromycin	Saquinavir	Amprenavir
Captopril		Amiodarone
Carvedilol	Other Agents	Ciprofloxacin
Clarithromycin	Boceprevir	Dronedarone
Conivaptan	Clarithromycin	Erythromycin
Cyclosporine	Itraconazole	Diltiazem
Diltiazem	Ketoconazole	Fluconazole
Dronedarone	Mibefradil	Fosamprenavir
Erythromycin	Nefazodone	Grapefruit juice
Felodipine	Posaconazole	Seville orange juice
Itraconazole	Suboxone	Verapamil
Ketoconazole	Telithromycin	Voriconazole
Quercetin	Telaprevir	
Quinidine	Troleandomycin	
Ranolazine		
Tacrolimus		
Verapamil

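### The French protocol is inconsistent on whether azithromycin is permitted on study, and it omits the exception, warning and timing advice that AMC Section 4.4.4 supplies

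*Combined protocol and SAP*

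**What the plan says.** Five places in the French protocol bear on this.

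- **Section 10.10.3 (MAC prophylaxis)**: "Azithromycin 1,200 mg PO once weekly must be initiated for prophylaxis" when the CD4 count drops under 50. An expected fall below that level during chemotherapy is also a trigger.
- **Appendix 21.9**: "Strong CYP3A inhibitors and P-glycoprotein inhibitors must be discontinued 7 days prior to therapy". Azithromycin stands in the P-glycoprotein column with no mark or footnote.
- **Section 8.1, criterion 20**: P-glycoprotein inhibitors are among the listed agents, and "If patients are taking any of these excluded medications, they must be discontinued at least 7 days (1 week) prior to the initiation of" chemotherapy. The synopsis repeats this.
- **Section 10.9, item 7**: among the items to record on the concomitant medication forms is "Receipt of disallowed medications (CYP3A4 or P-glycoprotein inhibitors) after study enrolment, as per Appendix 20.9".
- **Section 10.8.1**: lists what is prohibited at enrolment and for the study's duration. It covers certain antiretrovirals and potent CYP3 inhibitors, and names neither P-glycoprotein inhibitors nor azithromycin.

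AMC Section 4.4.4 opens with the same requirement as French 10.10.3 and then goes further. It says that AMC Sections 3.1.19 and 7.3.7 and Appendix XIII make azithromycin a disallowed drug. It warns that "this may increase the chemotherapy drug exposure and contribute to increased toxicity". It then states: "This limited exception is permitted in the case of MAC prophylaxis". It ends by recommending particular days of each cycle. In AMC Appendix XIII, azithromycin carries an asterisk that leads back to 4.4.4.

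**The concern.** A French investigator whose patient's CD4 count is falling finds one section that requires azithromycin and three places that exclude its class or call it disallowed. Nothing in the French text says how they fit together. The AMC exception does not help, because it cites AMC section numbers only and sits in a document that a French site is not working from.

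Two things are at stake. The first is safety. An investigator who gives the drug under the French text does so without the warning and timing advice that AMC sites receive for the same regimen. The second is the record. The same prophylaxis is an authorised exception under one protocol and reads as receipt of a disallowed drug under the other. French Section 16.0 says that the two sets of data are analysed together, and toxicity is a secondary objective.

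**Working it through.** No sample size, error rate or event count is involved, so there is nothing to recompute. The check compares the texts.

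**Step 1. Compare the two protocols.**

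| Element | AMC protocol | French protocol |
|---|---|---|
| Azithromycin required at low CD4 | 4.4.4 | 10.10.3 |
| Class stopped 7 days before therapy | 3.1.19, Appendix XIII | 8.1 criterion 20, Appendix 21.9 |
| Class called disallowed after enrolment | 7.3.7 | 10.9 item 7 |
| Azithromycin in the P-glycoprotein column | Appendix XIII, with asterisk | Appendix 21.9, no mark |
| Exception for MAC prophylaxis | 4.4.4 | none |
| Exposure and toxicity warning for azithromycin | 4.4.4 | none |
| Recommended days | 4.4.4 | none |

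The first four rows match in substance, apart from the asterisk. The last three exist only on the AMC side. French 10.8.2 notes that MMAE is a P-glycoprotein substrate but does not mention azithromycin.

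**Step 2. Ask whether the French rules meet in time.** The explicit rule in criterion 20 and Appendix 21.9 is a washout before therapy. The trigger in 10.10.3 is a fall in CD4 during chemotherapy. For the most part these apply at different times. They can overlap, because 10.10.3 also acts on an expected fall, and that judgement can be made before cycle 1.

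**Step 3. Ask what bars the drug after treatment starts.** Only 10.9 item 7 suggests a bar, by calling the class disallowed in a list of what to record. Section 10.8.1, whose purpose is to state such prohibitions, does not name the class. So the French text points both ways. AMC 4.4.4 reads its own near-identical passages as disallowing azithromycin on protocol, which shows that the restrictive reading is a natural one.

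**Step 4. Check the cross-references.** Section 10.9 and criterion 20 point to Appendix 20.9, but the appendix is numbered 21.9. Criterion 20 also cites 3.1.16, which is an AMC section number.

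**Step 5. Bound the size.** France plans 20 of the 51 participants, so the number affected lies between 0 and 20. Criterion 15 requires an entry CD4 count of at least 100 and a viral load below 50 copies/ml, so only participants whose count falls, or is expected to fall, from at least 100 to below 50 are concerned. The documents give no rate for this. AMC Section 10.3 and Appendix XIV report unpublished preliminary data in which CD4 rose about one month after treatment in nearly all subjects, but that does not describe the lowest count during treatment. The number is probably small and may be zero.

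**The case against.** The strongest reply is that a French site can comply with every literal instruction. The washout ends when therapy starts, 10.8.1 imposes no on-study ban on this class, and 10.9 only lists what to record. The wording in 10.9 is also loose: it calls CYP3A4 inhibitors disallowed although criterion 20 and the appendix allow moderate ones with caution. A site could give azithromycin under 10.10.3, record it under 10.9, and break nothing. There are also partial safeguards: the study chair or co-chair reviews concomitant medications before enrolment, and the French and American coordinators discuss adverse events every two months.

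Much of this stands, and it limits the point. A reader might infer that French sites are bound to violate one rule. The documents do not support that, because no French passage states an operative on-study prohibition. A reader might also infer that the AMC team regarded its timing as essential. AMC 4.4.4 only recommends those days, and it says that exposure may increase, not that it will.

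The reply does not remove the inconsistency. Calling a class disallowed after enrolment while requiring a member of it needs an explanation, and the AMC team thought near-identical wording needed one. The safeguards do not replace it: the medication review comes before enrolment, whereas the trigger usually comes later, and the calls discuss events that have already happened.

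**Conclusion.** Wrong as written, minor. The French protocol is internally inconsistent on whether azithromycin is permitted on study, and it lacks the exception, warning and timing advice that the AMC protocol supplies for near-identical wording.

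The conclusion rests on the French text as supplied, in which no exception appears. The missing asterisk is unlikely to be a loss in conversion from PDF, because the matching AMC table kept its mark.

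A reader might infer that pooled toxicity will differ by country. The documents do not support that: the data are pooled, Section 16.3 plans no stratification, no country comparison is planned, and the number affected cannot be derived. The sample size of 51 and the primary PFS analysis are unaffected. What remains is a gap bearing on the safety of a few participants, or possibly none, and on how their medication is classified.

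**What to change.** Amend the French protocol so that Section 8.1 criterion 20 (and its copy in the synopsis), 10.8.1, 10.9, 10.10.3 and Appendix 21.9 agree with one another and with AMC 4.4.4. The amendment should state whether azithromycin for MAC prophylaxis is permitted on study, and whether the AMC exception, warning and timing advice apply to French sites. If they apply, Appendix 21.9 needs a footnote like the one in AMC Appendix XIII. In the same amendment, change the references to Appendix 20.9 to 21.9. Which clinical rule should stand is for the sponsor and the coordinating investigators to decide.

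The cost is a short amendment and, where applicable, one table footnote, with the usual ethics and authority review. No extra data collection or change to the analysis is needed, because 10.9 already requires receipt of these drugs to be recorded.

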10.10.4 Pre-infusion prophylaxis

Pre-infusion prophylaxis (e.g., diphenhydramine) may be administered per institutional guidelines.

11.0 STUDY PROCEDURES

11.1 Registration and inclusion procedure

After it has been determined that the subject is eligible and an informed consent has been signed by the subject, the subject must be registered on-line via the AMC AdvantageEDC_{SM} Internet Data Entry System (AdvantageEDC). Enrollment and data collection will occur via the AMC Internet Data Entry System.

The participating site will ensure a subject meets all eligibility criteria prior to completing the protocol-specific eligibility checklist in AdvantageEDC for enrolment. Subjects will be enrolled on-line via AdvantageEDC no more than 1 week prior to the initiation of treatment (enrollment 1 day prior to or on the day of treatment is strongly encouraged). Once the eligibility checklist is submitted a system-generated confirmation email will be sent to the enroller upon successful completion of the subject enrollment. If the on-line system is inaccessible, the site should notify the AMC ODMC (via email at [contact] or via phone at 001 [contact]) for further instructions.

The investigator should fax ([contact]) at the same time the following documents: anonym copy of the pathology report (see appendix 20.7). The LYSARC coordination center ([contact]) will be the contact for any request.

11.2 Pathological diagnosis

The pathological diagnosis of Hodgkin lymphoma should have been performed locally before the inclusion for each patient.

Histopathology central review process has become in the last years a common and prerequisite procedure for clinical trials in the field of lymphomas. A mandatory pathological review will therefore be organized for all patients included in the trial at diagnosis. The goal of this central review will be to confirm the diagnosis and to precise its classification according to the WHO classification 2008.

The pathological review will be centralized at the LYSA-Pathology (LYSA-P) institute, Hôpital Henri Mondor, Créteil. For each patient, the investigator will be requested to join with the form of inclusion a copy of the anonymised histopathological report where the name and address of the pathologist having diagnosed the lymphoma will be easily identified as well as a copy of the bone marrow report.

All requested tumor paraffin embedded blocks from the formalin fixed sample (that have been used for diagnosis), or 10 unstained slides will be sent to the LYSA-P, according to the process described in Appendix 20.7 "Pathological samples review". At reception, routinely stained sections will be performed and an appropriate panel of antibodies according to morphological aspects will be applied. A pathological review, performed by at least 2 experts hematopathologists will be organized at the LYSA-P and a consensus diagnosis will be established. A LYSA-P pathological report will then be sent to the clinical coordinator and to the initial pathologist.

Initial tumor block will also be used to make tissue microarray (TMA) and DNA/RNA extraction.

11.3 Biological study/ samples

Blood samples will be collected at inclusion and sent to Bicêtre hospital. The specific informed consents must be signed before any sample procedure. These samples will be integrated in a comprehensive collaborative studies. This may include proteomic, genetic, virological and immunology studies.

The samples processing is described on Appendix 20.7.

The following sample will be collected at baseline, before treatment:

- For proteomic (plasma storage for protein analyses): 10mL (2 tubes) of blood on Heparin Lithium tubes (provided by LYSARC).
- For genetic (cells storage for DNA extraction): 10mL (2 tubes) of blood on EDTA tubes
- For immunology and virological studies (EBV viral load in mononuclear cells and in plasma, analyse of immune response anti-EBV, cytokines analyses): 20mL (4 tubes) of blood on Heparin Lithium tubes (provided by LYSARC).

On the day of blood sampling, the sample will be sent at room temperature by carrier and centralized to the Bicêtre hospital.

12.0 STUDY COMMITTEES

12.1 Independent Data Monitoring Committee

An Independent Data Monitoring Committee (IDMC), including at least three independent members (2 experts in HL including 1 expert in VIH) will be established. The IDMC will meet periodically to review the safety and efficacy data from the trial.

More details about IDMC operation will be provided in the IDMC Chapter.

The first IDMC is planned to occur after the 1st SAE for hematologic or neurologic toxicity after the approval of this current version of protocol or after the completion of 4 cycles according of two first patients according this current version of protocol.

13.0 CRITERIA FOR PREMATURE DISCONTINUATION OF THE STUDY

13.1 Premature withdrawal from trial intervention

After enrollment, subjects will be permanently withdrawn from study treatment for any of the following reasons. In the event of withdrawal from treatment, the reason for study treatment removal and the date the subject was removed must be documented in the Off Protocol Treatment Form in AdvantageEDCSM. See Section 9.6 on evaluations to be performed at early discontinuation of therapy.

- 1. Participants who experience a delay of over 7 days in cycle 1 will be removed from the study. For subsequent cycles, if two sequential doses of AVD + BV or AVD alone are held due to unresolved toxicity, leading to a treatment delay of an additional 2 weeks (i.e., 4 weeks between doses), the participant will be taken off protocol therapy. The participant will be followed for survival and may resume AVD treatment off study.
- 2. Severe toxicities as outlined in Section 10.6.1.
- 3. Progressive lymphoma at any time while on study.
- 4. Voluntary withdrawal.
- 5. The investigator has the right to remove subjects from study for clinical reasons which he or she believes to be life threatening or resulting in significant morbidity to the subject.
- 6. Any subject who develops HBV reactivation or acute Hepatitis B as defined by the reappearance of a previously suppressed hepatitis B surface antigen, a positive IgM hepatitis B core antibody, and a positive viral load. Any patient with Hepatitis B or C who has worsening liver function as defined by Section 10.6.2 will also be removed from study.
- 7. Any subject who on repeat PFT is found to have a DLCO when corrected for anemia less than 70%.
- 8. Subjects who become pregnant or breast-feed.
- 9. Subjects with progressive disease at the end of cycle 2 will be removed from study treatment, while patients with stable disease may be removed from the study treatment at the discretion of the local responsible investigator. Progressive or stable disease defined at cycle 2 will be based by CT criteria only, as FDG-PET has yet to be validated in HIV-associated HL.
- 10. If found by central pathology review to not have the diagnosis of HL.
- 11. If the subject has had two cycles of AVD + brentuximab vedotin and develops recurrent Grade 3 peripheral neuropathy despite dose reductions of brentuximab vedotin and vinblastine, the subject may continue the study receiving AVD with dose adjustments in vinblastine as clinically necessary, keeping in mind to maintain the dose and schedule as in standard therapy, or may be removed from protocol treatment. This decision will be at the discretion of the investigator.

